7.5 Missing Data

The term missing date refers to a completely missing date or to an incomplete date/partial date where parts are not available, e.g., missing month/day/year.

If there is missing data for a categorical summary, there will be a row showing the number and percentage of subjects with missing values.

7.5.1 Missing Start and End Dates

Missing adverse event (AE) start dates will be imputed conservatively, i.e., missing values will be imputed in such a way that the duration of the AE is considered with the longest possible duration and such that, whenever the AE may potentially start after first date of study drug, the AE will be handled as a treatment-emergent adverse event (TEAE).

Whenever a medication may potentially start prior to ZX008 treatment and end after Visit 1, that medication will be assumed to be prior and concomitant (i.e., assume it started prior to ZX008 treatment in Study 1900 and continued into the treatment period).

The partial/missing start date of an AE or prior/concomitant medication will be imputed for the purpose of calculating TEAE status and prior/concomitant medication status. Definitions are provided in the following table. Imputed dates will not be presented in the listings.

Partial/	Adverse	Missing day – If day is missing but month and year are
Missing Start date	Event	present, then impute the 1 st of the month, unless month
	RUR	is same as month of Visit 1, in which case impute Visit 1 date. Missing day and month – If day and month are both missing but year is present, then impute 1 st January, unless year is the same as year of Visit 1, in which case impute Visit 1 date.
	* 0° 0	Completely missing – If start date is completely missing, then impute Visit 1 date.
Call	you and	Note: if these rules lead to imputing a start date after a known end date, impute 1 st January of the year of the end date.
nen'i ca	Prior and Concomitant	Missing day – If day is missing but month and year are present, then impute the 1 st of the month.
OCALINOPI	Medication	Missing day and month – If day and month are both missing but year is present, then impute 1 st January.
		Completely missing – If start date is completely missing, then impute whichever is earlier from: 1 st January of the same year as the end date (if the year of end date is known) or Visit 1 date minus 1 day.

Version 4.0 Confidential Page 23 of 59

Zogenix International L	3 27 October 2023		
Statistical Analysis Plan	Fenflur	ramine Hydrochloride	ZX008-1900/EP0215
			o imputing a start date after a start January of the year of the
		end date.	

Baseline

The baseline value will be the value collected at Visit 1, except for ECHOs. See CV SAP for details.

7.6.3 Open-label Extension (OLE) Treatment Period

The OLE Treatment Period covers the period during which subjects will receive open label treatment with ZX008 until approval of ZX008 has been obtained from regulatory authorities for the subject's indication and country of residence, until a managed access program is established, or until the investigational product development for the subject's indication is stopped by the Sponsor, whichever comes first.

7.6.4 **Post-dosing Period**

For subjects discontinuing from study treatment and not transitioning to commercial drug, the Post-dosing Period begins immediately at the end of OLE Treatment Period defined by EOS/ET Study Visit and extends for a planned 2 weeks. This includes the Taper Period, if applicable to

Zogenix International Limited, a wholly owned subsidiary of UCB 27 October 2023 Statistical Analysis Plan Fenfluramine Hydrochloride ZX008-1900/EP0215 the subject. The visit at the end of the Post-dosing Period is labelled "EOS/ET +14 days" in

outputs.

7.6.5 **Mean Daily Dose**

The mean daily dose for a subject, sometimes referred to as the actual mean daily dose, is the average dose of ZX008 in mg/kg/day taken by a subject between Visit 1 and the EOS/ET Visit.

The calculation of the mean daily dose is based on the actual dose of ZX008 and takes into account dosing rules that capped the amount of drug that could be taken in a single day.

The mean daily dose of ZX008 per subject during the OLE is calculated from the weighted average of the assigned daily dosages by the investigator during the study, and the number of days the subject was maintained at each dose level.

The following categories will be used to describe mean daily dose and will be presented in mg/kg/day:

• 0 - < 0.4• 0.4 - < 0.6• ≥ 0.6 On each day, the actual dose will be calculated as:

On each day, the actual dose will be calculated as:

- 1. Assigned dose level (mg/kg), if the subject's weight (kg) * assigned dose (mg/kg) was ≤ Maximum allowed dose or
- 2. 30 (mg) / weight (kg), if the subject's weight (kg) * assigned dose (mg/kg) was > Maximum allowed dose, if the subject was not on concomitant STP or
- 3. 20 (mg) / weight (kg), if the subject was on concomitant STP and the subject's weight (kg) * assigned dose (mg/kg) was > 20 mg.

The reasoning for this is that the maximum quantity to be given on any day is 30 mg for subjects not on concomitant STP and 20 mg for subjects on concomitant STP.

The mean daily dose of ZX008 per subject during the OLE will be calculated from the weighted average of the actual daily dosages and the number of days the subject remains on each actual dosage during the OLE Treatment Period.

More specifically, let Dose be a subject's initial actual dosage in the OLE. The subject will be assumed to remain compliant on that dosage until there is a documented change in dosage assigned by the investigator or until the EOS/ET visit. Let Days₁ be the number of day that the subject is assumed to be on that initial actual dosage. If a new actual dosage, Dose₂, resulting either from a change in assigned dosage or from a relevant change in the body weight and/or STP treatment, the subject will be assumed to continue at that dosage for the total number of days, Days₂, until another change in actual dosage is documented or the subject reaches the EOS/ET visit.

The mean daily dose for a subject is then calculated as:

$$[(Dose_1 * Days_1) + (Dose_2 * Days_2) + + (Dose_n * Days_n)] / [Days_1 + Days_2 + + Days_n]$$

Zogenix International Limited, a wholly owned subsidiary of UCB 27 October 2023 Statistical Analysis Plan Fenfluramine Hydrochloride ZX008-1900/EP0215

where Dose_n and Days_n are the last assigned dosage and number of days spent on the last assigned dosage (up to and including the EOS/ET visit), respectively.

Special cases will be handled as follows:

- For subjects who terminate early but attend an ET visit, the calculation will assume subjects stayed on their last assigned dose from the time it was assigned until the time of the termination date or ET visit, whichever is said.
- For subjects who are lost to follow up and do not have an EOS/ET visit, the calculation will be based on the dosages and time spent in OLE up to and including their last on-treatment visit.
- For subjects who are lost to follow up prior to Visit 2, the calculation will use the initial assigned dosage as the subject's mean daily dose.

Volume (ml) should not be used to calculate the mean daily dose as it may lead to discrepancies.

If it is not possible to determine a subject's mean daily dose due to a lack of data, an additional "Unknown" mean daily dose group will be added to summary tables and listings.

7.6.6 **Modal Dose**

For each subject, the ZX008 dose administered on the greatest number of days during the Treatment Period is the modal dose for that subject.

Study Completion 7.6.7

A subject will have completed the study when they have completed 36 months of treatment (24 months in Denmark) or have transitioned to commercial drug. A subject may continue in the study past 36 months of treatment if ZX008 has not yet been approved from regulatory authorities for the subject's indication and there is no managed access program available to the subject.

A subject will be considered to have completed 36 months of treatment (24 months in Denmark) if the EOS/ET visit (last on-treatment visit for subjects lost to follow-up without an EOS/ET visit) falls on Study Day 1050 or later (Study Day 690 or later in Denmark).

EFFECTIVENESS ASSESSMENTS 8

All effectiveness assessment analyses will be performed on the mITT Population. Results will be summarized in tables and presented in a subject listing. The summaries will be presented overall and by seizure disorder (Dravet syndrome or LGS) for the following visits: Months 6, 12, 18, 24, 30, 36, and Last On-Treatment Visit.

Improvement in Seizure Burden

Based on discussions with the parent/caregiver, clinical evaluation, and review of an optional seizure diary, the percent improvement in seizure burden will be assessed by the investigator using one of the following: <25%, $\ge25\%$, $\ge50\%$, $\ge75\%$, 100% (i.e., seizure-free) improvement. The number and percentage of subjects in each of the 5 categories will be presented for each visit as compared to last visit. A two-sided 95% CI will be calculated for each percentage using the

Zogenix International Limited, a wholly owned subsidiary of UCB 27 October 2023 Statistical Analysis Plan Fenfluramine Hydrochloride ZX008-1900/EP0215

Clopper-Pearson method. Figures will show the percentage of subjects in each category at each visit overall and by seizure disorder (Dravet syndrome or LGS).

Note that at the start of the current trial, most subjects will have already been receiving ZX008 rilation for at least one year in an earlier, open-label trial, i.e., in a feeder study. Thus, the change in seizure burden in the current trial may not accurately reflect the full response to ZX008 treatment.

8.2 Clinical Global Impression – Severity & Improvement

As subjects entering Study 1900 have been treated in the prior open-label trial leading to some level of improvement, the CGI-Improvement score may show little movement (i.e., No Change).

The CGI-S questionnaire will be administered at Visit 1 to establish the baseline severity of disease and serve as a reference for assessing improvement over the course of the OLE. AS above, subjects were treated with ZX008 prior to baseline for this trial, and the severity ratings at baseline may reflect previous clinical improvement. CGI-S assessments will be made independently by both the investigator and parent/caregiver. The CGI-S may be repeated at later visits if there is a permanent change in the person making the assessment.

The CGI-S comprises 4 ratings (refer to Appendix 3 of the Clinical Study Protocol Amendment 4.0). The severity of a subject's condition overall (Global), and for each of the 3 more specific indicators of health (cognition, behavior, and motor abilities) will be rated on a 7-point scale ranging from 1 (normal, not at all ill) to 7 (among the most extremely ill) as follows:

ay ill

arkedly ill

6=severely ill

7=among the most extremely ill

S baseline characteristics will be per and percentage of subjected. Analogous static illes. The Enroll anges duri for the CGI-S baseline characteristics will be included in the Demographics table. Specifically, the number and percentage of subjects in each of the 7 categories of the overall CGI-S score will be presented. Analogous statistics will be presented for the 3 more specific indicators of health in the CGI-S. The Enrolled Population will be used for baseline characteristics for CGI-S. If the rater changes during the study, a new CGI-S rating of severity at Baseline will be performed to be used for the subsequent CGI-I evaluations. CGI-S ratings after Baseline will be provided in a listing.

The CGI-I will be assessed at each visit beginning at Visit 2 (6 months, except for France: 3 months) through the end of study and permits a global evaluation of the subject's improvement over time. The investigator and the parent/caregiver (independently) will perform four ratings each, one for the subject's condition overall, and three for the more specific indicators of improvement, in cognition, behavior, and motor abilities (refer to Appendix 4 of the Clinical Study Protocol Amendment 4.0).

27 October 2023

Statistical Analysis Plan Fenfluramine Hydrochloride

ZX008-1900/EP0215

The improvement of a subject's condition overall, and for each of the 3 more specific indicators of improvement (cognition, behavior, and motor abilities), is rated on a 7-point scale ranging from 1 (very much improved) to 7 (very much worse) as follows:

1=very much improved

2=much improved

3=minimally improved

4= no change

5=minimally worse

6=much worse

7=very much worse

that adequation the CC The investigator and the parent/caregiver each indicate the appropriate response that adequately describes how the subject's overall condition has improved or worsened relative to the CGI-S rating provided at baseline.

Frequency tables will be produced for each time point and will include the number and percentage of subjects rated in each category, along with an associated Clopper-Pearson twosided 95% CI.

Separate tables reflecting the ratings by the investigator and the parent/caregiver will be presented.

Figures will show the percentage of subjects in each category will be presented at each visit, overall and by seizure disorder (Dravet syndrome or LGS), for both ratings by the investigator and the parent/caregiver.

Categorical and subgroup presentations of CGI-1 analysis may include:

Categories:

Clinically meaningful improvement (1,

Improved (Score = 1, 2, 3)

Improved or No Change (Score = 1, 2, 3, 4)

Domains:

Global

Cognition

Behavior

Motor Abilities

Age groups:

2 - < 6 years

6 - < 12 years

12 - < 18 years

2 - < 18 years

 \geq 18 years

• Sex:

Male

Female

• Number of prior and concomitant antiepileptic medications used:

≤ 2

3

≥ 4 medications

The number of prior and concomitant antiepileptic medications used is defined as the number of unique different medications started prior to Visit 1 and ongoing at Visit 1 where the Anatomical Therapeutic Chemical (ATC) Level 2 code is "Antiepileptics". Different medications are those with different standardized medication names.

The global CGI-I score will also be summarized by subjects' CGI-S score obtained at Visit 1. Note that the CGI-S score obtained at Visit 1 should be used even if there is a more recent CGI-S score recorded. These summaries will not be presented by mean daily dose. For these summaries subjects will be aggregated into 1 of 3 categories based on CGI-S score:

- CGI-S = 1 or 2 (normal or borderline ill)
- CGI-S = 3 or 4 (mildly or moderately ill)
- CGI-S = 5, 6, or 7 (markedly, severely, or among the most extremely ill).

The relationship between global CGI-I in the current study and degree of improvement seen in the CGI-I feeder study will also be investigated. Tables will be produced that summarize CGI-I in the current study by subjects' CGI-I Global rating at the end of the feeder study and will be reported overall and by seizure disorder (Dravet syndrome or LGS). These summaries will not be presented by mean daily dose.

Individual subject data will be listed for the CGI-I scales as assessed by the investigator and parent/caregiver.

9 SAFETY ASSESSMENTS

Additional safety summaries may be produced by seizure disorder (Dravet syndrome or LGS) if warranted.

9.1 Disposition of Subjects

Disposition of all subjects in the SAF population will be summarized in a table overall and by seizure disorder (Dravet syndrome or LGS). The following information will be included: numbers and percentages of subjects who completed 12 months, 24 months, 36 months, or greater than 36 months of treatment, as appropriate; numbers and percentages of subjects who completed the study; and the numbers and percentages of subjects who discontinued the study

Zogenix International Limited, a wholly owned subsidiary of UCB 27 October 2023 Statistical Analysis Plan Fenfluramine Hydrochloride ZX008-1900/EP0215

and reasons for discontinuation. In addition to the EOS/ET Visit, completion of additional visits, such as the EOS/ET Follow Up Visit, may also be presented in the table.

The number and percentage of enrolled subjects included in each analysis population will be summarized in a table.

The completion status and reasons for the study and treatment discontinuation of subjects in the Enrolled population will be listed. Classification to analysis populations will also be presented in a listing by subject.

9.2 **Demographics and Other Baseline Characteristics**

Subject demographics and seizure disorder (Dravet syndrome or LGS) data will be collected at study entry.

A table will summarize demographics and baseline characteristics for the SAF Population overall and by seizure disorder (Dravet syndrome or LGS).

The following demographic and baseline characteristics will be summarized:

• Seizure disorder

• Feeder study

• Age in years at Visit 1

• Sex

• Race

• Ethnicity

• Height (cm) at Visit 1

• Weight (kg) at Visit 1

• BMI (body mass index) (kg/m²) at Visit 1

• Region: North America (including Naited States of America of America

- Region: North America (including United States of America [USA], Canada, Mexico), Europe, and Australia.
- Country

Age in years at Visit 1 will be recalculated as (date of Visit 1)-(date of birth)/365.25 for the continuous summary of age.

The CGI-S ratings by Investigator and by parent/caregiver will be summarized by subgroups (age, sex, and number of prior and concomitant antiepileptic medications used) separately from other demographics and baseline characteristics data using the Enrolled Population overall and by seizure disorder (Dravet syndrome or LGS).

The age categories used in the demographics table are:

- 2 <6 years
- 6 <12 years
- 12 <18 years

- 2 < 18 years
- >=18 years

ilation, Additionally, the age categories required by EudraCT and clinicaltrials gov will be used in the demographics table.

All subject demographic data will be listed for the Enrolled Population.

9.3 **Medical History and Ongoing Diseases and Conditions**

All subjects in the SAF Population who had prior medical history as per the CRF, will be listed by subject including subject number, description of the disease/condition, Medical Dictionary for Regulatory Activities (MedDRA) system organ class (SOC), MedDRA preferred term (PT), start date, and stop date (or ongoing if applicable). Additionally, subjects' medical history from prior studies will be carried over and ongoing AEs from the prior studies will be considered medical history unless there is an increase in the frequency or severity of the condition from the prior study, after the first dose of ZX008 in Study 1900 (assumed to be taken on Visit 1 date). In addition, any new clinically significant medical condition that occurred in prior studies will be entered as medical history.

AEs that occur after signing the ICF for this study, but before Visit 1 will be recorded as AEs in the prior study and medical history in Study 1900.

A medical history table will be produced for the SAF Population, displaying the number and percentage of subjects with any previous and ongoing medical history conditions by SOC and PT.

All medical history conditions and ongoing diseases and conditions will be coded using Version 21.1 or later of MedDRA.

A glossary of all medical history and ongoing diseases and conditions terms will be presented for the SAF Population. All medical history and ongoing diseases and conditions data will be listed for the SAF Population.

Epilepsy History 9.4

Seizure history may be recorded at Visit 1 and will be listed by seizure disorder (Dravet syndrome and LGS)

9.5 **Procedures**

Procedures (prior and concomitant non-medications, surgical history and concomitant procedures) will be listed for the SAF Population.

Physical and Neurological Examinations

Abbreviated physical and neurological examinations will be performed at Day 1 (Visit 1) and every 6 months thereafter as clinically indicated, as well as at the EOS/ET visit, the Follow-up visit (EOS/ET + 14 days) depending on last exam and AEs, and the Cardiac Follow-up visit (last dose + 6 months). Abbreviated physical and neurological examinations will also be performed at EOS/ET + 3 months and EOS/ET + 24 months in France, and at EOS/ET + 12 months in the UK. A full examination may be performed if warranted.

Zogenix International Limited, a wholly owned subsidiary of UCB 27 October 2023
Statistical Analysis Plan Fenfluramine Hydrochloride ZX008-1900/EP0215

Listings based on the SAF will be presented showing results from abbreviated physical and neurological examinations, for example if any abnormal findings and any clinically significant abnormal findings were present.

9.7 Vital Signs, Weight and BMI

Vital signs data are scheduled to be documented at each clinic visit according to the Schedule of Assessments for Subjects (refer to Section 16.1 of this SAP, Amendment 4.0, Amendment 4.1-FR, Amendment 4.1-UK tables). Vital sign measurements will include blood pressure, heart rate, temperature, and respiratory rate and observed values and changes from Baseline will be summarized and reported in tables for the SAF population.

Body weight and height are scheduled for collection at each clinic visit according to the Schedule of Assessments for Subjects (refer to Section 16.1 of this SAP, Amendment 4.0, Amendment 4.1-FR, and 4.1-UK tables). BMI will be recalculated during programming as weight (kg) / height (m)².

Age and sex-based z-scores for height and weight at each assessment will be determined using growth charts available from the Centers for Disease Control (CDC) and the World Health Organization (WHO). Details of the data sources are available at the following website, updated 09Jan2023.

https://www.cdc.gov/nccdphp/dnpao/growthcharts/resources/sas.htm

The Z-scores will be determined based on the subject's age in months at the date of assessment. For subjects with an incomplete birth date due to country requirements, January 1st of the provided year of birth will be assumed to be the date of birth. Age (in months) will be recalculated at each visit as [(date of visit) - (date of birth)]*12/365.25 for the calculation of z-scores. The z-scores will be determined only for subjects whose age at assessment is ≤ 20 years of age. Z-scores will be included in selected tables overall and split by syndrome (Dravet syndrome or LGS).

For weight the occurrence of at least a $\geq 7\%$ gain/reduction or $\geq 10\%$ gain/reduction from Baseline will be summarized in tables and reported for the SAF Population (overall and split by syndrome) by visit and at any time during the study.

Spaghetti plots will be used to summarize changes in weight. Plots of z-scores will be produced for each subject with $a \ge 7\%$ and $\ge 10\%$ change from Baseline in weight and will be displayed by visit.

For each vital signs, height, weight, and BMI parameter, observed values at each visit and change from baseline at each post-baseline visit will be summarized with descriptive statistics in a table for the SAF Population.

Listings of the markedly abnormal vital signs, weight, and BMI results will be provided by syndrome (Dravet syndrome or LGS). Markedly abnormal values are summarized in the table below:

Version 4.0 Confidential Page 32 of 59

Zogenix International Limited, a wholly owned subsidiary of UCB 27 October 2023

Statistical Analysis Plan Fenfluramine Hydrochloride ZX008-1900/EP0215

Statistical Allarysis				ZA008-1900/EF0213
Parameter	Age Group	Abnormally	Abnormally	Change Criteria
	(Years)	Low	High	
Weight (kg)	All			≥7% reduction/gain from baseline
	All			≥10% reduction/gain from baseline
Heart Rate (beats /minute)	2	< 87	> 150	Absolute Change from baseline > 20 bpm
	3	< 82	> 146	Absolute Change from baseline > 20 bpm
	4-5	< 77	> 142	Absolute Change from baseline > 20 bpm
	6-7	< 71	2137	Absolute Change from baseline > 20 bpm
	8-11	< 66	C 129	Absolute Change from baseline > 20 bpm
	12-14	₹61 ×0	\$121	Absolute Change from baseline > 20 bpm
	15-17	S57 et	> 115	Absolute Change from baseline > 20 bpm
	18-100	260	> 100	Absolute Change from baseline > 20 bpm
SBP (mmHg)	2-4	< 85	> 100	Absolute Change from baseline > 20 mmHg
Chu ₆	5-11	< 90	> 110	Absolute Change from baseline > 20mmHg
900 36,	12-17	< 100	> 120	Absolute Change from baseline > 20 mmHg
	18-100	< 90	>130	Absolute Change from baseline > 20 mmHg

Version 4.0 Confidential Page 33 of 59

Zogenix International Limited, a wholly owned subsidiary of UCB 27 October 2023
Statistical Analysis Plan Fenfluramine Hydrochloride ZX008-1900/EP0215

Parameter	Age Group	Abnormally	Abnormally	Change Criteria
	(Years)	Low	High	
DBP (mmHg)	2-4	< 40	> 64	Absolute Change from baseline > 10 mmHg
	5-11	< 51	> 75	Absolute Change from baseline > 10 mmHg
	12-17	< 61	> 80	Absolute Change from baseline > 10 mmHg
	18-100	< 60	> 85	Absolute Change from baseline > 10 mmHg
BMI (kg/m²)	2-17	≤ 20	≥ 25	13,013
	18-100	≤ 20	>30	
Respiration Rate (breaths/min)	2	< 18	> 42	
	3	< 18	≥ ₄₀ <	
	4-5	₹ 17 × O	€37	
	6-7	EBO TE	> 35	
	8-11	< 15	> 31	
	12-14	Q 13	> 28	
	15-17	< 13	> 26	
N.C	18-100	< 12	> 20	
Temperature (Celsius)	АН	≤ 36	≥ 38	> 4

Vital signs, weight, height, z-scores, and BMI data will be presented for the SAF Population in a listing. Electrocardiogram and ECHO Analysis of ECGs and Doppler ECHOs will be included in a separate CV SAP from ERT (formerly Biomedical Systems).

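### Setting every incomplete birth date to 1 January overstates age by up to a year, so height and weight z-score levels of affected, still-growing children are biased downward

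*SAP*

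**What the plan says.** SAP 9.7 (Vital Signs, Weight and BMI) introduces the measure: "Age and sex-based z-scores for height and weight at each assessment will be determined using growth charts" from the CDC and WHO. On the age to be used it says: "The Z-scores will be determined based on the subject's age in months at the date of assessment". Age in months is the visit date minus the birth date, in days, times 12/365.25, recalculated at each visit.

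For birth dates that are not fully available the section has one rule: "For subjects with an incomplete birth date due to country requirements, January 1st of the provided year of birth will be assumed". It gives no reason for choosing that day and provides no flag or sensitivity summary for z-scores obtained this way.

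The results have several uses. "Z-scores will be included in selected tables overall and split by syndrome". They are also plotted for each subject whose weight changes by at least 7% or 10% from Baseline, and they are listed for the Safety Population. There is an age limit: "The z-scores will be determined only for subjects whose age at assessment is ≤ 20 years of age".

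SAP 9.2 also calculates age at Visit 1 from the date of birth, but states no rule for an incomplete one.

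**The concern.** 1 January is one end of the range of possible birth days, not its middle. The error in age therefore has one sign and does not average out across children. A growing child who is treated as older than he or she is gets compared with taller and heavier peers, and the z-score falls. The cause is country requirements, so the affected subjects are likely to be grouped by country rather than scattered at random.

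Body weight and height are listed safety endpoints (protocol 2.3.1, SAP 3.3.1). Protocol 1.5.1 names decreased weight and decreased appetite among the most common adverse events in the controlled Dravet studies. The z-score is the age-referenced growth measure in the SAP. A one-sided error in its level looks like a growth deficit, and a reader of the outputs could not tell which values rest on an imputed birth date.

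**Working it through.** The documents state no figure on this point, so there is none to reproduce. The check applies the SAP 9.7 age formula to every possible birth day in a year.

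**Inputs from the SAP.** Age in months = (visit date - birth date) × 12/365.25. The imputed birth date is 1 January of the birth year.

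**Inputs assumed, because the documents do not give them.** Births are spread evenly over the year. Height growth is 2 to 8 cm/year with a reference SD of 4 to 7 cm. Weight gain is 5 to 15% per year with a coefficient of variation (CV) of 12 to 20%.

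**Step 1: age error.** The visit date cancels, so the error in months is (days from 1 January to the true birth date) × 12/365.25.

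- Smallest: born 1 January, 0.
- Largest: 364 × 12/365.25 = 11.96 months in an ordinary year; 365 × 12/365.25 = 11.99 in a leap year.
- Mean: 182 × 12/365.25 = 5.98 months; 182.5 × 12/365.25 = 6.00 in a leap year.

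The error is never negative.

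**Step 2: z shift per affected child.** For height, shift = -(growth per year × age error in years)/SD. For weight, shift = -ln(1 + annual gain) × age error in years/CV.

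| Measure | Assumption | Mean shift (0.5 year) | Largest shift (1 year) |
|---|---|---|---|
| Height | 2 cm/year, SD 7 cm | -(2 × 0.5)/7 = -0.14 | -0.29 |
| Height | 5 cm/year, SD 5.5 cm | -(5 × 0.5)/5.5 = -0.45 | -0.91 |
| Height | 8 cm/year, SD 4 cm | -(8 × 0.5)/4 = -1.00 | -2.00 |
| Weight | 5%/year, CV 20% | -(0.0488 × 0.5)/0.20 = -0.12 | -0.24 |
| Weight | 15%/year, CV 12% | -(0.1398 × 0.5)/0.12 = -0.58 | -1.16 |
| Either | no growth | 0 | 0 |

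The upper end pairs the fastest growth with the smallest SD, so it is a limit rather than a typical value.

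**Step 3: table mean.** If a share p of the children in a table is affected, its mean moves by p × the mean shift per child. The documents do not give p. For illustration, p = 10% gives 0.10 × (-0.14) = -0.014 to 0.10 × (-1.00) = -0.10 for height.

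**Step 4: change over time.** The birth-date error is the same number of days at every visit, so most of it cancels in within-subject change. A small drift can remain as growth rate and SD change with age. With an assumed 6.5 cm/year and SD 4.5 cm early, then 6 cm/year and SD 5.5 cm later, the mean shift goes from -(6.5 × 0.5)/4.5 = -0.72 to -(6 × 0.5)/5.5 = -0.55, an apparent change of about +0.18.

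**Step 5: age limit.** An assessment at a true age between 19 and 20 can receive an assigned age above 20, in which case it loses its z-score.

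**Step 6: mid-year alternative.** With 1 July imputed, the error runs from -5.95 months (-181 × 12/365.25; -5.98 in a leap year) to +6.01 months (183 × 12/365.25), with a mean of 0.02 to 0.03 months.

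**The case against.** The strongest reply is that this concerns a derived, descriptive output and an unknown, possibly very small, number of subjects. Neither document says how many birth dates are incomplete or in which countries. Observed height, weight and BMI, their changes from Baseline, and the 7% and 10% weight-change tables do not use the birth date. The study has one arm, and SAP 8.1 notes that most subjects had already received ZX008 for at least a year before entry. The z-score level therefore cannot show a drug effect by itself; within-subject change is more informative, and it is mostly protected. The error also leans towards overstating a growth deficit, not hiding one. All of this stands, and it limits the importance of the point. It does not make the levels right for the affected children.

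Three stronger readings are tempting, but the documents do not support them.

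- *The rule throws away a known birth month.* SAP 7.5 counts as missing "an incomplete date/partial date where parts are not available", and SAP 7.5.1 has a branch for event and medication dates that opens "If day is missing but month and year are" present, whereas SAP 9.7 has no such branch. But SAP 9.7 speaks of the provided year of birth, which reads naturally as year-only records. Nothing shows a birth date recorded with a month. This is a gap in the wording, not a demonstrated loss of data.
- *The z-score tables are off by several tenths of an SD.* That size applies per affected growing child, under assumed growth and SD. The shift in a table depends on the affected share, which is not given, and on age: the age groups include 12 to under 18 and 18 and over, and the bias shrinks towards zero as growth stops.
- *The weight-loss safety assessment is distorted.* The tables of weight and percent weight change do not depend on age.

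**Conclusion.** The point holds as a minor one. Under SAP 9.7 the age used for z-scores is too high by 0 to about 12 months whenever the birth date is incomplete, with a mean of about 6 months if births are spread evenly. The direction of the bias follows from the rule alone: z-score levels of affected children who are still growing are too low.

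Its size rests on assumptions. With growth of 2 to 8 cm/year and an SD of 4 to 7 cm, the mean height shift per affected child is about -0.14 to -1.00. With a gain of 5 to 15% per year and a CV of 12 to 20%, the mean weight shift is about -0.12 to -0.58. Both approach 0 when growth ends, and a table mean moves by these amounts times an unknown share. Some assessments at a true age of 19 to 20 also drop out, at an age when growth is small. No inference and no primary output changes.

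**What to change.** In SAP 9.7, replace 1 January with 1 July of the birth year when only the year is provided. Add that the 15th of the month is used should a month ever be provided; the age error would then lie between -0.46 and +0.53 months. Use the same imputed birth date for age at Visit 1 in SAP 9.2, so that one child does not have two ages. Flag z-scores that rest on an imputed birth date in the listing. Repeating the z-score table without those subjects is optional, and worth doing only if they turn out to be more than a few.

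Mid-year imputation brings the mean age error to about zero and halves the largest error. It cannot make an individual year-only value exact, which is why the flag is useful.

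The cost is a short SAP edit in two sections and a small programming change, with no new data. If earlier outputs used 1 January, the final z-scores may differ from them; a footnote can explain that.
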